For analysis purposes, the efficacy period will also be adjusted to account for large intervals between injections resulting from missing data. A large interval is defined as >28 days between any 2 adjacent BIVV001 injections within a prophylactic treatment regimen, and any such intervals will be removed from the efficacy period. The efficacy period prior to each such interval will end at the time of the last injection prior to the interval and restart at the time of the next prophylaxis injection. The efficacy period will be adjusted for each identified interval that is not within a surgical/rehabilitation period.

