4.4.1.4 Subgroup analyses

To assess the homogeneity of the treatment effect across various subgroups, analyses of the ABR will be performed across the following subgroups (categories with fewer than 5 participants may be combined with other categories):

- By bleeding phenotype at Baseline (estimated bleeds in prior 12 months, 0, >0-5, >5-10, >10)
- By number of target joints (none present, ≤ median of number present, > median of number present)
- By dosing and dosing interval compliance (<80%, $\ge80\%$)

The estimated mean ABR and the corresponding 95% CI will be provided, for each subgroup, using the same method as applied to the primary analysis. Forest plots will be provided.

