4.7.1.2 Compliance

Compliance will be assessed during the efficacy period and will be summarized for the FAS by age cohort and overall. Except for doses administered in the clinic, study treatment may be administered by the participant or a caregiver. Data from the eCRF and ePD will be considered for the analysis of treatment received and participants' compliance with the study protocol.

Compliance of prophylaxis injections

The compliance rate of each participant during the efficacy period will be calculated in 2 ways: As dose compliance and as dosing interval compliance. Compliance will first be determined on a per-injection basis and then on a per-participant basis. That is, compliance for an individual dose or dosing interval will be determined and then the overall percentage of doses and dosing intervals that were in compliance will be determined for each participant. For the purpose of evaluating compliance, the following will be considered per injection:

- The nominal dose taken compared to the study dose (50 IU/kg for prophylaxis treatment)
- The actual day of treatment compared to the study day of treatment (weekly for prophylaxis treatment)

An individual dose will be considered compliant if it is within 80%-125% of the study dose (50 IU/kg). An individual dosing interval will be considered compliant if the time between two prophylactic doses is within 36 hours of the study dosing interval (7 days).

The actual dosing intervals will be calculated as the length of time between consecutive prophylactic doses that are not separated by a bleeding episode or surgical/rehabilitation period (date / time of dose_{x+1} – date / time of dose_x). The actual time between doses will be determined in minutes and converted to days as the number of minutes divided by 1440. The absolute value of the difference between the actual dosing interval and the study dosing interval of 7 days must be ≤ 1.5 day (+/-36 hours) in order to be compliant.

All prophylactic injections will be used to determine prophylactic dose compliance; only the prophylactic dosing intervals that are not separated by a bleeding episode or surgical/rehabilitation period will be used to evaluate prophylactic interval compliance. Large injection intervals as defined in Section 4.1.1.2 will be included in the interval compliance calculation. Dose and dosing interval compliance rates per participant will be determined as follows:

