where the percentage of a study dose is calculated as: (nominal dose taken / study dose) \times 100.

Dose interval compliance rate =
$$\frac{\text{Number of doses taken within +/-36 hours of}}{\text{Study day/time}} \times 100$$

Both participant dose and dosing interval compliance rates will be summarized as continuous variables using descriptive statistics as well as categorically (<80%, $\ge80\%$) for the FAS.

A participant is considered "dose compliant" or "dosing interval compliant" if his respective rate is at least 80%. Based on this, participants will be further classified into the following mutually exclusive categories for overall compliance to their prophylactic treatment as:

- Both dose and interval compliant
- Dose compliant or interval compliant (but not both)
- Neither dose nor interval compliant

Compliance of ePD contemporaneous data entry

Injections (for prophylaxis or a bleed) and untreated bleeds must be entered into the ePD within 7 days from the date of the injection or the untreated bleed. Injections or untreated bleeds entered outside the 7-day window will be reported as protocol deviations. Descriptive statistics of the percentage of the participants with fewer than 80% of their total individual ePD records entered within this 7-day window and those with \geq 80% of records meeting this criterion will be presented for the FAS as well as a summary of % compliance to this criterion by participant.

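### Neither compliance rate falls in proportion to missed doses, and a bleed can erase a late interval, so the ABR-by-compliance subgroup can misclassify children with clustered gaps or rates near 80%

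*SAP*

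**What the plan says.** SAP 4.7.1.2 (Compliance) sets two per-participant rates over the efficacy period.

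- **Dose compliance** is the share of prophylactic injections given that lie within 80% to 125% of 50 IU/kg.
- **Interval compliance** rests on this definition: "The actual dosing intervals will be calculated as the length of time between consecutive prophylactic doses that are not separated by a bleeding episode" or a surgical/rehabilitation period. An interval complies if it is within 36 hours of 7 days, that is, 5.5 to 8.5 days.

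Both are shares of what was observed: "the overall percentage of doses and dosing intervals that were in compliance will be determined for each participant". For intervals, "only the prophylactic dosing intervals that are not separated by a bleeding episode or surgical/rehabilitation period will be used to evaluate prophylactic interval compliance". Long gaps stay in: "Large injection intervals as defined in Section 4.1.1.2 will be included in the interval compliance calculation". A child is compliant on either measure "if his respective rate is at least 80" percent, and the best overall class is compliance on both.

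SAP 4.4.1.4 then lists an ABR subgroup "By dosing and dosing interval compliance", split at 80%. SAP 4.1.1.2 treats long gaps differently when it builds the ABR denominator: "A large interval is defined as >28 days between any 2 adjacent BIVV001 injections within a prophylactic treatment regimen", and such intervals are cut from the efficacy period.

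The dose formula and the denominator of the interval formula are not legible in the text available. The prose of 4.7.1.2 supports counts of injections given and of intervals, and the check below uses those.

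**The concern.** A missed dose creates no interval of its own. It only lengthens the interval it falls in, and that interval fails once however long it becomes. Missed doses do not enter dose compliance at all. The interval rate therefore measures how many separate lapses occurred, not how much prophylaxis was missed, and it is most lenient when the misses come in long runs.

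The bleed rule adds a second problem. If a dose is already overdue and the child then bleeds, the interval leaves the rate and the lateness goes with it. If the bleed was treated and lies in the efficacy period, it still counts in ABR. The variable that splits the ABR subgroup then depends partly on the outcome being compared.

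At stake is the ABR-by-compliance subgroup, the planned analysis that sets adherence against bleeding. Children who missed a good deal of prophylaxis can sit on the compliant side of the forest plot.

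**Working it through.** The plan gives no worked compliance rate, so there is no figure to reproduce. The check is direct counting.

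**Inputs.** 52 weekly slots (52 weeks of once-weekly dosing, protocol synopsis); on time means 5.5 to 8.5 days; threshold 80% (both SAP 4.7.1.2). Assumption: every dose outside the gaps is on time and within the dose limits.

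**Formulas.** Let *c* be the on-time intervals, *f* the gaps and *g* the length of each gap in weeks. Count each interval by the dose that ends it.

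- c + g·f = 52
- SAP interval rate = c / (c + f)
- doses missed = (g − 1)·f
- doses taken / expected = (c + f) / 52

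**Step 1. Most doses that can be missed at a rate of 80% or more, with equal gaps**

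| Gap length | f | c | SAP rate | Missed |
|---|---|---|---|---|
| 14 days (single misses) | 8 | 36 | 36/44 = 81.8% | 8/52 = 15.4% |
| 21 days | 7 | 31 | 31/38 = 81.6% | 14/52 = 26.9% |
| 28 days | 6 | 28 | 28/34 = 82.4% | 18/52 = 34.6% |

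**Step 2. The same 18 missed doses in different patterns**

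| Pattern | SAP rate | Doses taken / expected |
|---|---|---|
| 18 single misses | 16/34 = 47.1% | 34/52 = 65.4% |
| nine 21-day gaps | 25/34 = 73.5% | 34/52 = 65.4% |
| six 28-day gaps | 28/34 = 82.4% | 34/52 = 65.4% |
| one 19-week gap | 33/34 = 97.1% | 34/52 = 65.4% |

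The SAP rate runs from 47% to 97% for the same number of missed doses, and the longest interruption scores best. In each pattern dose compliance can be 100%, because only the doses given are judged.

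**Step 3. Effect of dropping an interval that contains a bleed**

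- Nine 14-day intervals and 34 on time: 34/43 = 79.1%, non-compliant. If one late interval contains a bleed, it is dropped: 34/42 = 81.0%, compliant.
- Eight 14-day intervals: 36/44 = 81.8%, compliant without any bleed.
- Twelve 14-day intervals: 28/40 = 70.0%. Five of them must contain a bleed to reach 28/35 = 80.0%.
- If the dropped interval was on time, the rate falls slightly: 36/44 = 81.8% becomes 35/43 = 81.4%.

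**The case against.** The strongest defence concerns the bleed rule. Protocol 6.1.3 can hold back the next prophylactic dose until 72 hours after a 50 IU/kg bleed dose. It also has a child who bleeds when prophylaxis is due inject 50 IU/kg, and protocol 8.1.2 has that injection recorded as bleed treatment where the bleed needed treating. A child who follows the protocol can thus show a 14-day interval between doses labelled prophylactic. Leaving such intervals out is reasonable, although the SAP does not give this reason. The defence does not cover an interval that was already late before the bleed began.

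Three stronger readings are tempting, and the documents do not support them.

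- *A child who misses about 35% of doses is compliant.* This holds only if the misses cluster in gaps of about four weeks or more. As single misses or 21-day gaps, the same total fails.
- *Bleeds after late doses fall in the compliant subgroup.* The exclusion changes class only near 80%. A gap over 28 days between adjacent injections is cut from the efficacy period, so a bleed inside it leaves ABR too. A bleed-treatment injection may split a longer prophylaxis gap into shorter pieces, in which case the bleed can stay in. Six 28-day gaps that each contained a bleed would score 28/28 = 100%, but a treated bleed normally brings its own injection, so those would not be four weeks without drug.
- *The SAP always overstates compliance.* Ten single misses score 32/42 = 76.2% under the SAP rule but 42/52 = 80.8% on doses taken over expected. Here the SAP rule is the stricter one.

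Missed doses are also partly visible elsewhere. SAP 4.7.1 lists every dose, and 4.7.1.1 summarises injections by reason and exposure days by category. A child with about 34 exposure days would fall in the 25 to <50 category. None of these summaries compares doses given with doses expected, or feeds the ABR subgroup.

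**Conclusion.** The point holds in a conditional form. Neither rate falls in proportion to missed doses, so a child whose misses cluster can miss up to 18 of 52 doses (34.6%) in equal gaps of 28 days, and more in longer gaps, and still be classed compliant on both measures. Separately, a bleed in an already late interval can move a child near the threshold into the 80%-or-more ABR subgroup, so that grouping depends partly on the outcome.

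This rests on 52 weekly slots, all other doses on time and within the dose limits, and interval counts as the denominator. How many children would be affected cannot be told from the documents.

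The consequence is small. All analyses are descriptive, and the outputs affected are the compliance table and one ABR subgroup. Any compliance subgroup is defined after baseline, so a better rate improves the classification but does not make the comparison causal.

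**What to change.** Add to SAP 4.7.1.2 a per-participant rate of prophylactic doses taken divided by doses expected, specified as follows.

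- **Expected doses.** Count them on calendar time over the treatment period, excluding PK and surgical/rehabilitation periods but keeping gaps over 28 days. Dividing efficacy-period days by 7 would not work, because SAP 4.1.1.2 removes those gaps. Six 29-day gaps take out 174 of 364 days, which leaves 190/7, or about 27 doses expected, against about 33 taken.
- **Interval.** Use the participant's assigned interval: 7 days, or the shortened interval that protocol 6.1.2 allows in the younger cohort.
- **Bleeds.** Credit a bleed-treatment dose that replaces a due prophylactic dose, and do not score a protocol-directed delay as late. For an interval containing a bleed, score lateness only if the prophylactic dose was already more than 36 hours overdue at bleed onset.

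Report this rate beside the existing two and use it, with the 80% cut-off, for the ABR-by-compliance subgroup in 4.4.1.4. The child with six 28-day gaps then scores 65.4% and is non-compliant. The child with nine 14-day intervals scores 43/52 = 82.7%, and dropping a bleed interval no longer decides the class.

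The cost is SAP wording and one derivation from dosing dates and times already collected. Compliance figures may look less favourable for children with clustered gaps.

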4.7.2 Adverse events

General common rules for adverse events

Summaries of adverse events will be presented by age cohort as well as overall for the Safety Analysis Set.

All adverse events will be coded using the version of Medical Dictionary for Regulatory Activities (MedDRA) in effect at Sanofi at the time of database lock.

The primary focus of adverse event reporting will be on treatment-emergent adverse events (TEAEs). TEAEs are AEs that developed, worsened or became serious during the treatment-emergent period. Pretreatment adverse events will be listed separately.

An AE with incomplete or missing date/time of onset (occurrence, worsening, or becoming serious) will be classified as a TEAE unless there is definitive information to determine it is a pre-treatment AE. Details on classification of adverse events with missing or partial onset dates are provided in Appendix 3 (Section 5.3).

TEAEs that occurred during major surgical/rehabilitation periods will be included in the overall (top-line) summary of TEAEs but not in any of the other TEAE tables. The exception to this rule is that TEAEs occurring during a major surgical/rehabilitation period with an onset date on the day the surgical/rehabilitation period starts or on the day of the surgery (whichever comes earlier) will be included in the TEAE summaries. Consideration is given to AEs with an onset date at the start of the surgical/rehabilitation period in the event the pre-surgical dose was administered the day before the surgery.

TEAE incidence tables will present by system organ class (SOC) and preferred term (PT).

Listings will be provided for all AEs, SAEs, AEs resulting in discontinuation of study treatment and/or from the study, and deaths. AEs that are emergent prior to the first BIVV001 treatment, AEs that are emergent during a major or minor surgical/rehabilitation period, and AEs that are emergent on the day the major surgical/rehabilitation period starts will be flagged.

Analysis of all adverse events

Overall summary of treatment-emergent adverse events

An overall (top-line) summary of TEAEs will be provided which summarizes number of TEAEs, treatment-emergent serious adverse events (TESAEs) and treatment emergent adverse events of special interest (TEAESI) and (%) of participants with any: TEAE, related TEAE, TESAE, related TESAE, TEAESI, related TEAESI, TEAE leading to death, and TEAE leading to treatment discontinuation.

Analysis of all treatment-emergent adverse events

The following TEAE summaries will be generated for the safety population.

- TEAEs by SOC and PT
- TEAEs by PT in descending order of incidence
- TEAEs by relationship, presented by SOC and PT. AEs with a missing relationship will be counted as "Related" in the summary table, as described in Appendix 3 (Section 5.3). A participant will be counted once for each SOC and PT based on the highest relationship within that SOC and PT, respectively.
- TEAEs by maximal severity, presented by SOC and PT. AEs with a missing severity will be counted as "Severe" in the summary table, as described in Appendix 3 (Section 5.3). A participant will be counted once for each SOC and PT based on the greatest severity within that SOC and PT, respectively.

Analysis of all treatment emergent serious adverse event(s)

- TESAEs by SOC and PT
- TESAEs by PT in descending order of incidence
- TESAEs by relationship and SOC and PT

Analysis of all treatment emergent adverse events of special interest

- TEAESIs by SOC and PT
- TEAESIs by relationship and SOC and PT

Analysis of all treatment-emergent adverse event(s) leading to treatment discontinuation

• TEAEs leading to treatment discontinuation, by SOC and PT

Analysis of treatment-emergent adverse event(s) occurring during a major or minor surgical/rehabilitation period

- All TEAEs occurring during a major or minor surgical/rehabilitation period will be provided in a listing. The following categories will be flagged separately:
 - TEAEs occurring during a major surgical/rehabilitation period, excluding AEs with an onset date on the day the surgical/rehabilitation period starts

- TEAEs occurring during a major surgical/rehabilitation period with an onset date on the day the surgical/rehabilitation period starts
- TEAEs occurring during a minor surgical/rehabilitation period

Subgroup analysis

- All TEAEs will also be provided by demographic factors including: race (White, Black, Asian, Other), geographic location (Asia/Pacific, Europe, North America)

Analysis of deaths

A listing of AEs with an outcome of death will be provided.

Embolic and Thrombotic Events

The occurrence of embolic and thrombotic events will be described by age cohort and overall. The analysis will consist of a search of TEAE data using the Embolic and Thrombotic Events Standard MedDRA Query (SMQ). Medical adjudication of the search results will also be performed according to the following definition:

- Embolic and thrombotic events are defined as arterial or venous thrombosis, confirmed by imaging
- Coronary artery thrombosis/occlusion must be confirmed by coronary angiography to be included as part of medical adjudication
- Thrombosis involving the cerebral vasculature must be confirmed by imaging such as magnetic resonance imaging venogram (MRV), computed tomography venogram (CTV), magnetic resonance angiography (MRA), or computed tomography angiography (CTA) to be included as part of medical adjudication
- An indwelling central venous access device is a well-established risk factor for thrombosis (2) and thrombotic events associated with such devices will not be included as part of medical adjudication. Occlusion or malfunction of a central venous access device also will not be included as part of medical adjudication
- Infusion thrombophlebitis is a recognized complication of peripheral vein infusion (3) and will not be included as part of medical adjudication

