	 Number and type of blood component transfusions used during perioperative period for major surgery
	 Estimated blood loss during perioperative period for majo surgery
 To evaluate the safety and tolerability of BIVV001 treatment 	 The occurrence of adverse events (AEs) and serious adverse events (SAEs)
	 The occurrence of clinically significant changes from baseline in physical examination, vital signs, and laboratory tests
	The occurrence of embolic and thrombotic events
• To assess the PK of BIVV001 based on the one-stage activated partial thromboplastin time (aPTT) and two-stage chromogenic FVIII activity assays	 PK parameters including, but not limited to, maximum activity (C_{max}), elimination half-life (t_{1/2}), total clearance (CL), total clearance at steady state (CL_{ss}), volume of distribution at steady state (V_{ss}), area under the activity time curve (AUC), dose-normalized area under the activity-time curve (DNAUC), mean residence time (MRT), incremental recovery (IR), trough activity (C_{trough}), time above predefined FVIII activity levels
Tertiary/Exploratory	
 To assess the impact of BIVV001 treatment on caregiver- and/or patient-reported clinical outcome assessments measurements and 	 Changes in PROMIS-SF Physical Function measures from Baseline to Week 52 (≥8 years old) and via parent proxy version (≥ 5 years old)
health resource utilization	 Changes in PROMIS Pain Intensity measures from Baseline to Week 52 (≥8 years old) and via parent proxy version (≥ 5 years old)
	 Changes in PROMIS Pediatric-SF Pain Interference measures from Baseline to Week 52 (≥8 years old) and via parent proxy version (≥ 5 years old)
	• Changes in EuroQoL 5-dimension 5-level Youth (EQ-5D-Y) from Baseline to Week 52 (≥8 years old) and via parent proxy version (4-7 years old)
	Caregiver interviews at Week 52 (or subsequent post- study follow-up visit)
	Changes in healthcare resource utilization

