4.1 GENERAL CONSIDERATIONS

Unless otherwise specified, all data will be summarized for each age cohort (<6 years and 6 to <12 years) and overall.

The surgery subgroup will be included in baseline tables as well as the overall AE summary. When the surgery subgroup is included in a summary table, participants who participated in the surgery subgroup will be included in the columns for age cohort and the surgery subgroup but will only be counted once in the overall column.

Baseline

Baseline is defined as the last non-missing measurement taken prior to the first dose of study drug, excluding measurements taken during a surgical/rehabilitation period. For HJHS, if there are no measurements taken prior to the first dose of the drug, and the first measurement is taken no more than 7 days after the first dosing, then this first measurement will be considered as baseline for HJHS.

Study Day

Study day is defined as the number of days relative to the date of the first dose of study drug. The first dose of study drug is Day 1. Study day will be calculated as (date of event – first dose date +1) if the date of event is on or after the first dose date or (date of event – first dose date) if the date of event is before the first dose date. If the date of event is missing or partial, the corresponding study day will be left blank.

Exposure Day

One exposure day (ED) is defined as a 24-hour period in which a participant receives 1 or more doses of study drug, with the time of the first injection of study drug defined as start of the ED.

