4.1.1 Definition of study periods

This section defines the study periods used for different analyses, including treatment period, efficacy period, surgical/rehabilitation period, and safety period.

All analyses and summaries relating to bleeding and consumption will be based on the *efficacy period* (Section 4.1.1.2); data collected during the PK and surgical/rehabilitation periods (major and minor) will not be included.

All other efficacy analyses will be based on the *treatment period* (Section 4.1.1.1), excluding data that occurs during any major surgical/rehabilitation period to avoid confounding the treatment effect. Analysis of efficacy endpoints that are visit-based will not include visits that are coincidental with a major surgical/rehabilitation period.

Surgical evaluations will be based on the *surgical/rehabilitation period* (Section 4.1.1.3).

All safety analyses will be based on the *safety period* (Section 4.1.1.4). Unless otherwise specified, adverse events and laboratory evaluations occurred during major surgical/rehabilitation periods will not be included in the safety summaries.

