4.1.1.3 Surgical/rehabilitation period

The broadest span of time for the surgical/rehabilitation period is from the first dose of BIVV001 given for the surgery (ie, the pre-surgery dose) up to 1 minute before the first regular prophylactic dose after the last day of postoperative care/rehabilitation.

Since not all participants will have these events, specific considerations for the start and end of the surgical/rehabilitation period are as follows:

Start of the surgical/rehabilitation period:

- If there is more than one pre-surgical dose, then the first one should be selected (a presurgical dose can be administered on the day or the day before surgery).
- If there is no pre-surgical dose but there was a prophylactic dose, or a dose given for "OTHER" reason prior to the surgery on the day of or the day before surgery, then the last of these doses should be selected.
- If there is no pre-surgical dose or no prophylactic dose on the day before surgery, then select the start date/time of the surgery. If the time was not recorded, then select the date and impute 00:01 for the time.

End of the surgical/rehabilitation period:

- If the participant resumed the prophylactic regimen following the surgical/rehabilitation period, then the end of the surgical/rehabilitation period is 1 minute before the first regular prophylactic dose after the latest date and time among the following (impute 23:59 if time is not available): 1) discharge from the hospital, 2) end of perioperative period follow-up phone call, and 3) end of a two-week period (one-week for minor surgeries) after the resumption of weekly prophylaxis treatment.
- If the participant did not resume the prophylactic regimen following the surgical/rehabilitation period (eg, the participant received no further prophylactic doses), then the end of the surgical/rehabilitation period is imputed as 23:59 on the last date among the following: 1) discharge from the hospital, 2) end of perioperative period follow-up phone call, and 3) end of a two-week period (one-week for minor surgeries) after the last surgical dose.

Statistical Analysis Plan BIVV001-EFC16295 23-Aug-2021 Version number: 1

• If the overall end of study is declared while the participant is still in the surgical/rehabilitation period, then select the date of the end-of-study visit and impute 23:59 for the time if a time is not provided.

Two exceptions are noted:

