4.7 SAFETY ANALYSES

The summary of safety results will be presented by age cohort as well as overall for the Safety Analysis Set. The analysis of the safety variables will be essentially descriptive, and no systematic testing is planned.

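### TEAEs that start after the first day of a major surgical period are missing from every detailed TEAE table, and possibly from the embolic/thrombotic analysis

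*SAP*

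**What the plan says.** SAP 4.1.1 sets a default for all safety analyses. Unless the SAP states otherwise, adverse events in major "surgical/rehabilitation periods will not be included in the safety summaries".

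SAP 4.7.2 makes one allowance: TEAEs from major "surgical/rehabilitation periods will be included in the overall (top-line) summary of TEAEs but not in any of the other TEAE tables". It then keeps in the TEAE summaries those events with onset on the day the surgical period starts or the day of surgery, whichever is earlier. The other tables are TEAEs by SOC/PT, by relationship and by severity, together with the tables of serious events (TESAE), events of special interest (TEAESI) and events leading to discontinuation.

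The denominator is not reduced to match. SAP 4.7 states "The summary of safety results will be presented by age cohort as well as overall for the Safety Analysis Set", and SAP 4.7.2 introduces its tables with "The following TEAE summaries will be generated for the safety population".

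Surgical-period events remain visible in two places. One is the top line, which has a surgery column (SAP 4.1: "The surgery subgroup will be included in baseline tables as well as the overall AE summary"). The other is a set of flagged listings.

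For thrombosis, SAP 4.7.2 says "The analysis will consist of a search of TEAE data using the Embolic and Thrombotic Events Standard MedDRA Query (SMQ)", followed by medical adjudication. It does not mention surgical periods. "The occurrence of embolic and thrombotic events" is a secondary safety endpoint in SAP Table 2, and Protocol 8.3.7 also makes such events an AESI.

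**The concern.** AE and SAE occurrence and embolic/thrombotic events are secondary safety endpoints. The rule takes from the detailed tables the events of a period in which exposure can be higher than under weekly prophylaxis (Protocol 6.1.4), and in which the protocol itself permits short-term thromboembolic prophylaxis (Protocol 6.5).

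Two things are at stake:

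- **Reconciliation.** The top line can show a serious or special-interest event that no SOC/PT table names, although both use the same population.
- **An ambiguous endpoint.** Two programmers following the SAP could reach different counts of embolic/thrombotic events. One would apply the SAP 4.1.1 default and drop a perioperative event. The other would read a search of TEAE data as covering all TEAEs and keep it.

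**Working it through.** The plan gives no figure to reproduce on this point. The check is a reading of the rules, followed by illustrations.

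**1. What the exception keeps.** Under SAP 4.1.1.3 the surgical period starts with a dose on the day of surgery or the day before, or otherwise with the surgery itself. The start is therefore never later than the day of surgery, and the earlier of the two days is always the first day of the period. If the pre-surgical dose is given the day before, an event on the day of surgery is itself left out of the detailed tables.

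**2. Whether the embolic/thrombotic subsection overrides the default.** It does not say so. The SAP writes such an override where it wants one: SAP 4.3.1 expressly includes inhibitor samples taken in surgical periods. It also tabulates surgical-period data separately where it wants that: SAP 4.2 presents major protocol deviations from major surgical periods apart from the rest. Neither is done for thrombotic events. Nothing in the TEAE definition excludes surgical-period onset either, so both readings remain open.

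**3. Whether the protocol requires the exclusion.** Protocol 9.4.3 plans AE incidence by SOC/PT with no exclusion for surgery. It is described as a summary (9.4.1), so it does not forbid one. Protocol 8.1.7 excludes surgical-period data, but it sits under efficacy assessments, names bleeding episodes and follow-up time, and covers minor as well as major surgery. It does not settle the AE question.

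**4. Effect of one event.** Assume 65 dosed and one participant with a post-operative TEAESI and no other event in that row.

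- Top line: 1/65 = 1.5% (Clopper-Pearson 95% CI 0.04% to 8.3%). Detailed table: 0/65 (0% to 5.5%).
- In a cohort of 25: 1/25 = 4.0% against 0/25.
- Surgery column of the top line, with an assumed 1 to 10 operated participants: 1/10 = 10% to 1/1 = 100%.
- If the participant already has another event in the row, the participant percentage does not change.

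**5. Length of the excluded period.** For a major surgery after which prophylaxis resumes, the period runs at least to the "end of a two-week period (one-week for minor surgeries) after the resumption of weekly prophylaxis treatment".

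- Floor: 14/364 = 3.8% of 52 weeks.
- Assume that prophylaxis resumes 3 to 21 days after the first surgical dose, that the next regular dose follows the two-week mark by 0 to 7 days, and that discharge and the follow-up call are not later. The range is then 3 + 14 + 0 = 17 days (17/364 = 4.7%) to 21 + 14 + 7 = 42 days (42/364 = 11.5%).
- Share of all person-time, for 1 to 10 surgeries in 65 participants: 1 × 17/(65 × 364) = 0.07% to 10 × 42/(65 × 364) = 1.8%.

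**6. Exposure in the period.** Protocol 6.1.4 allows additional doses of 30 or 50 IU/kg every 2 to 3 days. While that interval is used, this is 30 × 7/3 = 70 to 50 × 7/2 = 175 IU/kg per week, against 50 for prophylaxis (1.4 to 3.5 times). The same section allows dosing to be spaced out after the first post-operative week, so this range need not hold for the whole period.

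**The case against.** The rule is explicit, pre-specified and in line with the handling of laboratory values and vital signs. The trial is single-arm and descriptive, and no test depends on these tables. The events are not hidden: the top line counts TEAEs, TESAEs and TEAESIs and gives participant percentages for serious, special-interest, fatal and discontinuation events. Surgical-period TEAEs have their own flagged listing. With few operated participants, a listing identifies each event as well as a table would. A thrombotic event is an AESI and would be in the top-line TEAESI row on either reading. Expedited reporting and DMC oversight do not depend on these tables. Confounding by surgery is also a fair reason to show results without these periods.

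All of this stands, and it limits the severity. The numbers of surgeries and the period lengths used above are assumptions, and even so the person-time is small. The thrombotic part is an ambiguity, not a stated omission, and the permission for thromboembolic prophylaxis is not evidence of an expected signal.

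It does not answer the main point. Followed exactly, the SAP can print 0/65 in a serious or special-interest SOC/PT table beside 1/65 in the top line. Confounding justifies an additional view without surgical periods, but not leaving these events out of every SOC/PT table.

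**Conclusion.** The concern holds and should be fixed. That TEAEs with onset after the first day of a major surgical period are absent from all detailed TEAE tables is the direct effect of SAP 4.7.2. That they might also be absent from the embolic/thrombotic analysis follows from silence there combined with the SAP 4.1.1 default; the text does not settle it.

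The effect is on the completeness and reconciliation of secondary safety endpoints. It is zero without such an event, one participant per affected row with one (1.5% of 65 or 4.0% of 25, under the assumptions above), and small for overall AE rates.

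**What to change.** Amend SAP 4.1.1 and 4.7.2 as follows:

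- State that the embolic/thrombotic analysis and the TESAE, TEAESI and discontinuation tables include all TEAEs in the safety period, regardless of surgery.
- Give the general TEAE table by SOC/PT with and without major surgical periods, or add one SOC/PT table for surgical periods, so that it reconciles with the top line.
- Optionally, if day-of-surgery events are meant to be kept when the pre-surgical dose falls on the day before, define the exception as running from the period start day through the day of surgery, and align the listing flags.

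The cost is SAP wording and a few table rows, from data already collected. Reported AE rates may be slightly higher and include events due to surgery; the version without surgical periods shows by how much and keeps the sponsor's preferred view.
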